#### **4.6 Per-protocol Set 2 (PP2)**

Per-protocol Set 2 is defined as subjects in the Full Analysis Set who complete 8 weeks of treatment with lanthanum carbonate and who have serum phosphate assessment data available to allow summarizing the percentage of subjects achieving age-specific KDOQI target. Subjects who have serum phosphate levels above the age-specific KDOQI targets prior to the start of lanthanum carbonate treatment will be included in this set. Further details are described in the Evaluable Subjects Determination Plan which can be found in Section 21.

Subjects who experienced hypophosphatemia, that lead to temporary interruption or discontinuation of treatment before the 8-week phosphate assessment, are considered compliant with the 8 week treatment requirement (as treatment dosed per-protocol, Section 6.2.1) and can thus be included in the PP2, PP1, and SCS analysis populations.

In previous versions of the protocol, a Per-protocol (PP) Set, defined as consisting "... of all Subjects in the FAS who complete Part 2 (ie, subjects who have a visit 2.8 serum phosphorus assessment) and do not have any pre-defined major protocol deviations that may affect the primary efficacy variable" was the only analysis set created to summarize efficacy endpoints. Following Protocol Version 6.0 (Amendment 5), two PP sets: PP1 and PP2 were defined.

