### **Hypophosphatemia During Parts 2 and 3**

(See [APPENDIX 2](#) for guidelines on phosphate and calcium level management.)

If the serum phosphate is <4mg/dL (1.29mmol/L) for adolescents aged 12-18 years, or <4.5mg/dL (1.45mmol/L) for subjects aged 10 years to <12 years, we advise that the Investigator monitor the phosphate levels carefully and consider reducing the binder dose by 25% depending on the rate at which the phosphorus is falling when prior laboratory testing is reviewed.

If the serum phosphate is <3.5mg/dL (1.13mmol/L) for adolescents aged 12-18 years, or <4mg/dL (1.29mmol/L) for subjects aged 10 years to <12 years, the binder should be stopped and serum phosphate levels monitored closely.

The binder should be resumed at 50% of the prior dose when the serum phosphorus is >4mg/dL (1.29mmol/L) for adolescents, and >4.5mg/dL (1.45mmol/L) for subjects aged 10 years to <12 years.

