## 9.5 Selection of Subjects to be Included in the Analyses

**Screened Set** – The set of subjects who have signed informed consent.

**Enrolled Set** – Subjects who have signed informed consent and have begun some study procedures (eg, dispensed investigational product, current drug has been withdrawn).

**Safety Analysis Set 1** – Enrolled subjects who have taken 1 dose of investigational product in Part 1 and who have completed at least 1 follow-up safety assessment.

**Safety Analysis Set 2** – Enrolled subjects who have taken 1 dose of investigational product in Part 2 or Part 3 and who have completed at least 1 follow-up safety assessment.

It is noted that safety assessments from the period when a subject is exposed to calcium carbonate will be summarized for calcium carbonate treatment. Safety assessments from the

period when a subject is exposed to lanthanum carbonate will be summarized for lanthanum carbonate treatment.

**Safety Completer Set (SCS)** – Subjects who receive at least 8 weeks of lanthanum carbonate treatment from either Part 2 or Part 3 of the study.

**Full Analysis Set (FAS)**–Subjects who have taken at least 1 dose of investigational product and who have at least 1 phosphate assessment during Part 2 or Part 3.

**Per-protocol Set 1 (PP1)** – Subjects in the Full Analysis Set who complete 8 weeks of calcium carbonate treatment followed by 8 weeks of lanthanum carbonate treatment and who have serum phosphate assessment data available to allow summarizing the percentage of subjects achieving age-specific KDOQI target. Only subjects who have serum phosphate levels equal to or above the age-specific KDOQI targets at study entry and between the calcium carbonate treatment and lanthanum carbonate treatment at Visit 2.4 will be included in this set.

**Per-protocol Set 2 (PP2)** – Subjects in the Full Analysis Set who complete 8 weeks of treatment with lanthanum carbonate and who have serum phosphate assessment data available to allow summarizing the percentage of subjects achieving age-specific KDOQI target. Subjects who have serum phosphate levels equal to or above the age-specific KDOQI targets prior to the start of lanthanum carbonate treatment will be included in this set.

**Pharmacokinetic Set 1** - Subjects in the Safety Analysis Set 1 for whom the primary pharmacokinetic data are considered sufficient and interpretable. Subjects in Part 1 who vomited may be excluded from Pharmacokinetic Set 1.

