#### **4.3.3 Safety Completer Set (SCS)**

The Safety Completer Set is defined as subjects who receive at least 8 weeks of lanthanum carbonate treatment from either Part 2 or Part 3 of the study.

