## 21. APPENDIX

### 21.1 Evaluable Subject Determination Plan

#### 1. Definition of Evaluable Subject in Per-Protocol Analysis Set 2 for Primary Endpoint Assessment

For the purposes of the primary endpoint assessment, at least 32 subjects, who complete 8 weeks of treatment with lanthanum carbonate and are assessable for baseline and 8 weeks serum phosphate level, will be required. Approximately 65 subjects may be enrolled to acquire at least 32 evaluable subjects. In order to prevent over enrolment, subjects' evaluability status will be assessed and confirmation of achieving at least 32 evaluable subjects will be performed.

The criteria that subjects must meet to determine eligibility include:

- Aged 10 years to <18 years of age at the time of consent
- Confirmed serum phosphorus level drawn prior to commencing Lanthanum therapy in Part 2 or Part 3 of the clinical trial (Baseline Phosphorus)
  - Subjects who participated in Part 2a and received calcium carbonate, baseline serum phosphorus must be drawn after a washout period of up to 3 weeks
- Baseline serum phosphorus levels above KDOQI recommendations:
  - Age <12 years: Serum phosphorus >6.0mg/dL (1.94mmol/L)
  - Age ≥12 years and older: Serum phosphorus >5.5mg/dL (1.78mmol/L)
- Demonstration of 8 weeks of Lanthanum therapy
- Confirmed serum phosphorus level after 8 weeks of Lanthanum therapy
- Both baseline and 8 weeks serum phosphorus levels are assessed at the same lab (central or local lab)
- Subjects, who received lanthanum carbonate therapy in part 2 or part 3 but did not receive 8 weeks of continuous treatment because of temporary dose interruption due to hypophosphatemia (protocol Appendix 2: guidelines for phosphorus and calcium levels), will be considered evaluable, if they satisfy other criteria mentioned above (eg baseline phosphate > KDOQI target).

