## 1.2 Data Sources for Assessment of Evaluability

Evaluability Assessment will be performed on the subject level analysis data set (one record per subject) created through the steps described in section V.

Evaluability is determined if the following conditions are met

1. If subject is not a screen failure
2. Baseline Phosphate data is not missing, and baseline phosphate is  $\geq$  KDOQI Target
3. Week 8 Phosphate data is not missing

OR

Phosphate value missing at Week 8, but early termination shows hypophosphatemia (Protocol Appendix 2: guidelines for phosphorus and calcium levels).

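### SAP 4.6 allows subjects who discontinued lanthanum before 8 weeks for hypophosphatemia into the Safety Completer Set, which SAP 4.3.3 and protocol 9.5 define as at least 8 weeks received

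*SAP*

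**What the plan says.** SAP 4.3.3 defines the Safety Completer Set as "subjects who receive at least 8 weeks of lanthanum carbonate treatment from either Part 2 or Part 3 of the study". Protocol 9.5 uses the same words: "Subjects who receive at least 8 weeks of lanthanum carbonate treatment from either Part 2 or Part 3 of the study". Neither place states an exception.

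SAP 4.6 defines Per-protocol Set 2 and then adds a rule for low phosphate. It covers "Subjects who experienced hypophosphatemia, that lead to temporary interruption or discontinuation of treatment before the 8-week phosphate assessment". These subjects "are considered compliant with the 8 week treatment requirement (as treatment dosed per-protocol, Section 6.2.1"). On that basis the SAP opens three sets to them: "and can thus be included in the PP2, PP1, and SCS analysis populations". The protocol section it cites says that below a phosphate threshold "the binder should be stopped and serum phosphate levels monitored closely", and that dosing resumes once phosphate has recovered.

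The Evaluable Subject Determination Plan (SAP 21.1) carries the rule for PP2. One criterion admits subjects who "did not receive 8 weeks of continuous treatment because of temporary dose interruption due to hypophosphatemia". Its section 1.2 also accepts the case "Phosphate value missing at Week 8, but early termination shows hypophosphatemia". Section 2 of that plan has a matching interruption rule for PP1. The plan does not mention the SCS.

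SAP Section 17, the list of changes from the protocol, describes the SCS as subjects who received 8 weeks of lanthanum. The exception is not listed there.

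**The concern.** The SCS is defined by how long the drug was taken. A subject who stopped lanthanum for good before 8 weeks has not had 8 weeks of it, whatever the reason. SAP 4.6 nevertheless allows that subject in. Its reason is that dosing followed the protocol. That is an argument about adherence. It can support membership of a per-protocol efficacy set, but it does not add exposure in a set defined by exposure.

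The SCS supplies tables for exposure and compliance (SAP 8.1 and 8.2), adverse events (11.1), laboratory data (11.2), vital signs (11.3) and ECG (11.4). SAP Section 17 says the set was added after discussions with the PDCO, and the amended sample size text says the focus of the study moved to safety. A reader will take SCS results as results in subjects treated for at least 8 weeks, and under SAP 4.6 that need not be true of every subject in them.

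The exception is also hard to find. It sits under the PP2 heading, so someone building the SCS from 4.3.3 would not see it. Because it says only that such subjects can be included, two programmers could build different sets from the same SAP.

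**Working it through.** The plan states no figure that depends on SCS membership, so the check is mainly a comparison of definitions. The nearest figure is the safety sample size in SAP 2.5. The probability of at least one event at a true rate of 5% in 32 subjects is 1 − 0.95^32 = 0.806, which reproduces the stated 80.6%. The protocol's version is 1 − 0.95^35 = 0.834, which reproduces its 83.4%. Neither figure is tied to the SCS, so neither settles the question.

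**Step 1: the measure of duration.** SAP 8.1 counts exposure as last dose − first dose + 1 and makes no deduction for gaps. Eight weeks is 8 × 7 = 56 days, which is also the target day in SAP 21.1.

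**Step 2: apply both rules to each kind of subject.** The stopping times are illustrations placed at scheduled visits. The documents report none.

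| Subject | Duration by SAP 8.1 | SAP 4.3.3 | SAP 4.6 |
|---|---|---|---|
| Low phosphate; paused at Week 4, resumed at Week 6, last dose day 56 | 56 − 1 + 1 = 56 days | In | May be in |
| Low phosphate; stopped for good, last dose day 28 | 28 − 1 + 1 = 28 days; 28/56 = 50% | Out | May be in |
| Low phosphate; stopped for good, last dose day 14 | 14 − 1 + 1 = 14 days; 14/56 = 25% | Out | May be in |
| Another reason; stopped for good, last dose day 28 | 28 days | Out | Out |

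The first row shows no conflict, because the subject qualifies without the exception. The second and third rows are the contradiction. The fourth shows that the exception is selective: two subjects with equal exposure are treated differently according to why they stopped.

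**Step 3: does another section resolve it?** SAP 21.1 applies the rule to PP2 and, for interruptions, to PP1, but not to the SCS. SAP Section 17 lists a change as small as above versus equal to or above the phosphate target for PP1 and PP2, yet omits this one. Protocol 9.5 has no such exception. Nothing reconciles 4.3.3 with 4.6.

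**Step 4: size.** With k such subjects in an SCS of N, their share is k/N. The documents give neither k nor N, and k may be zero.

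**The case against.** The strongest case for the SAP is that the rule is pre-specified, openly stated and given a reason, and that its wording is permissive. The protocol's route for low phosphate is to stop, monitor and resume, and protocol 4.4.1 does not list hypophosphatemia among the criteria for removing a subject. The usual case is therefore a pause, and a paused subject can still reach 8 weeks. This stands, and it confines the point to permanent discontinuation. It does not remove the point, because SAP 4.6 names discontinuation and SAP 21.1 provides for early termination.

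Short exposure would also be visible. The SCS exposure table (Table 4.1.3) reports the minimum duration and has categories of ≤1, >1-4 and >4-8 weeks, and Listing 5.1.3 gives first and last dose dates. Adverse events, vital signs and ECG are summarised on Safety Analysis Set 2 as well. This stands too. It limits the harm, although the adverse event, laboratory and ECG tables on the SCS would not themselves show who had short exposure.

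Three stronger readings are tempting but not supported:

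- A reader might infer that every subject stopped for low phosphate is placed in the SCS. The text only permits inclusion, and those who resumed may belong there anyway.
- A reader might infer that these subjects dilute adverse event incidence. They have less time at risk, but they were stopped for a laboratory effect, and a clinically relevant laboratory change can itself be an adverse event (protocol 8.1.5). The net direction is not known.
- A reader might put each such subject at 1/32 = 3.1% of the set. The 32 is the minimum number evaluable for the primary endpoint in PP2, not the size of the SCS. The SCS has no baseline phosphate or Week 8 laboratory requirement and accepts Part 3 treatment, so it may be larger.

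**Conclusion.** The inconsistency is real and minor. For a subject who permanently stopped lanthanum before 8 weeks because of hypophosphatemia, SAP 4.3.3 and protocol 9.5 exclude and SAP 4.6 permits inclusion. The stated reason does not suit a set defined by treatment received, and Section 17 does not record the exception.

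The conclusion assumes that 8 weeks in SAP 4.3.3 is measured as in SAP 8.1, from first to last lanthanum dose. If continuous dosing were required instead, paused subjects would conflict as well, but 4.3.3 does not ask for that. The number affected is unknown and may be zero, and no direction of effect on SCS adverse event rates can be claimed. Safety Analysis Set 2 is unaffected, as is the sample size statement. No view is taken on the clinical stopping rule.

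**What to change.** Remove the SCS from the exception in SAP 4.6 and keep the exception for PP1 and PP2 only. State in SAP 4.3.3 that the 8 weeks are counted as last dose − first dose + 1, on lanthanum, across Parts 2 and 3. The second sentence is needed because SAP 8.1 words duration within each part, and because deletion alone would leave the status of a paused subject open.

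The threshold should be given in days. Part 2 visits have a window of ±3 days, so a subject who finishes at 56 − 3 = 53 days and does not enter Part 3 would fall below a strict 56. The SAP should say whether the window applies.

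The cost is a few words. The SCS may lose a few subjects, including some stopped for a drug-related laboratory effect, so SCS results should be read beside those of Safety Analysis Set 2, where these subjects remain. Some PP2 subjects may then fall outside the SCS.

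If the sponsor prefers to keep the exception, the minimum is to write it into SAP 4.3.3, list it in Section 17, and report how many SCS subjects had less than 8 weeks of lanthanum.

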#### **4.7 Pharmacokinetic Sets (PK Sets)**

##### **4.7.1 Pharmacokinetic Set 1**

The Pharmacokinetic Set 1 is defined in Section 12.1.

##### **4.7.2 Pharmacokinetic Set 2**

The Pharmacokinetic Set 2 is defined in Section 12.1.

## 5. SUBJECT DISPOSITION

**Part 1:** A summary table will be produced for all subjects showing the number of subjects screened and enrolled, in addition to the number and proportion of subjects in the Safety Analysis Set 1, subjects who completed Part 1, subjects who prematurely discontinued from Part 1 (also split by reason for withdrawal) and subjects who entered Part 2 (**Table 1.1.1.1**). This summary table will also be presented by age group ( $\geq 10$  to  $<12$  years,  $\geq 12$  to  $<18$  years). (**Table 1.1.1.2**)

### **Part 2 (2a and 2b):**

A summary table will be produced by treatment group, showing the number and proportion of subjects in the Safety Analysis Set 2 (including those who entered the study in Part 2b), subjects who completed Part 2, subjects who prematurely discontinued from Part 2 (also split by reason for withdrawal), subjects who entered Part 3 (prematurely or otherwise), including those who entered Part 3 due to hypercalcaemia during treatment with calcium carbonate in Part 2 (a), subjects in the FAS, PP1, PP2 and subjects in the SCS Set. (**Table 1.1.2.1**) This summary table will also be presented by age group ( $\geq 10$  to  $<12$  years,  $\geq 12$  to  $<18$  years). (**Table 1.1.2.2**)

### **Part 2a (Treatment Period 2), Part 2b and Part 3 Combined (Lanthanum Carbonate only):**

A summary table will be produced showing the number and proportion of subjects in Safety Analysis Set 2 who completed the study, who entered Part 3 due to hypercalcaemia during treatment with calcium carbonate in Part 2a (Treatment Period 1), subjects in the FAS, PP2, SCS Set and subjects who prematurely discontinued from the study (also split by reason for withdrawal). (**Table 1.1.3.1**) This summary table will also be presented by age group ( $\geq 10$  to  $<12$  years,  $\geq 12$  to  $<18$  years). (**Table 1.1.3.2**)

An enrolment summary will be presented by site, and by country, showing the first day of consent, and the last study completion/withdrawal date among all Enrolled Subjects, the duration of enrolment (in days) [calculated as (last date of contact for any subject at that site - the first date of informed consent for any subject at that site + 1)], and the number of subjects enrolled and in each subject population set. The number and proportion of subjects enrolled in total, by site, and by country will be summarised. For individual sites, the site location and primary investigator's name will also be presented. (**Table 1.1.4**)

A listing of all Screen Failures (ie, subjects who gave informed consent and failed to meet the inclusion and/or met at least 1 of the exclusion criteria and were not administered IP(s) as defined by the protocol) will be presented along with reasons for screen fail and details of any adverse events (AEs).

A listing of subject disposition (**Listing 1.1**) will be provided for all Enrolled Subjects, including the date of informed consent/assent, date of first dose and date of last dose for each part of the study (Part 1, Part 2, and Part 3) and each treatment group, accordingly (Part 2a: Calcium Carbonate, Part2a: Lanthanum Carbonate), date of completion/discontinuation, and whether the subject completed the study. Details of early terminations will also be listed for all Enrolled Subjects including the date of informed consent/assent, date of first dose and date of last dose for the part of the study (Part 1, Part 2, or Part 3) and treatment group, accordingly (Part 2a: Calcium

Carbonate, Part 2a: Lanthanum Carbonate or Part 2b: Lanthanum Carbonate) in which the subject withdrew, date of termination, duration of exposure (days), and primary reason for discontinuation as recorded on the termination page in the eCRF. **(Listing 1.2)** A listing of study analysis set classifications will be provided for all Enrolled Subjects specifying whether each subject was part of the defined analysis sets of Section 4, or not. **(Listing 1.3)**

## 6. PROTOCOL DEVIATIONS

**Part 1:** A summary of the number (and percentage) of all Safety Analysis Set 1 with any protocol deviations, as well as the categories of deviations, will be provided overall and by site. **(Table 1.5.1)**

**Part 2:** A summary of the number (and percentage) of subjects in the Safety Analysis Set 2 with any protocol deviations, as well as the categories of deviations, will be provided overall and by site for each treatment group. **(Table 1.5.2)**

**Part 2 and 3 combined (Lanthanum Carbonate only):** A summary of the number (and percentage) of subjects in the Safety Analysis Set 2 and SCS with any protocol deviations, as well as the categories of deviations, will be provided overall and by site. **(Table 1.5.3, Table 1.5.4)**

Protocol deviation data will be listed for all enrolled subjects. **(Listing 2.1.1)**

Evaluable subjects for the PP1 and PP2 Sets will be listed for the Full Analysis Set. **(Listing 2.1.2)**

## 7. DEMOGRAPHIC AND OTHER BASELINE CHARACTERISTICS

**Part 1:** Descriptive summaries will be presented for Lanthanum Carbonate for the Safety Analysis Set 1 (**Table 1.2.1.1.1**) and presented by age group ( $\geq 10$  to  $<12$  years,  $\geq 12$  to  $<18$  years). (**Table 1.2.1.1.2**)

**Part 2:** Descriptive summaries will be presented by treatment group for the Safety Analysis Set 2, the FAS, the PP1, the PP2 for lanthanum carbonate treatment only (Part 2a, Treatment Period 2 and Part 2b) additionally presented by age group ( $\geq 10$  to  $<12$  years,  $\geq 12$  to  $<18$  years) (**Table 1.2.1.2.1 to Table 1.2.1.4.2 and Table 1.2.1.5.1 and Table 1.2.1.5.2, respectively**).

**Part 2 and 3 Combined (Lanthanum Carbonate only):** Descriptive summaries will be presented for Lanthanum Carbonate for the SCS for 8 weeks of lanthanum carbonate treatment only, (**Table 1.2.1.6.1**) additionally presented by age group ( $\geq 10$  to  $<12$  years,  $\geq 12$  to  $<18$  years). (**Table 1.2.1.6.2**)

**Pharmacokinetic Set 1:** Descriptive summaries will be presented for PK Set 1 (**Table 1.2.1.7.1**), and additionally presented by age group ( $\geq 10$  to  $<12$  years,  $\geq 12$  to  $<18$  years). (**Table 1.2.1.7.2**)

**Pharmacokinetic Set 2:** Descriptive summaries will be presented for PK Set 2 (**Table 1.2.1.7.3**), and additionally presented by age group ( $\geq 10$  to  $<12$  years,  $\geq 12$  to  $<18$  years). (**Table 1.2.1.7.4**)

The following demographic characteristics will be summarised in the following order in the tables: age (years), age group (categorical:  $<10$  years,  $\geq 10$  to  $<12$  years,  $\geq 12$  to  $<18$  years and  $\geq 18$  years), sex, ethnicity, race, weight (kg), height (cm) and Body Mass Index ( $\text{kg}/\text{m}^2$ ). Continuous variables such as subject age, weight, and height will be summarised using number of observations, mean, standard deviation, median, minimum, and maximum values. Categorical variables such as the subject's sex, ethnicity, and race will be summarised using number of observations and percentages for each category. Please note that age will only be calculated when the date of birth is not partial. Age will be calculated as the difference between date of birth and date of informed consent or assent, which is usually signed at the beginning of the Screening Period.

Renal history will be summarised for each of the Safety Analysis Sets (Safety Analysis Set 1, Safety Analysis Set 2 and the SCS) for each Part of the study (**Table 1.2.2.1 [Part 1], Table 1.2.2.2 [Part 2], Table 1.2.2.3 [Part 2 and 3 combined]**), including the number and proportion of subjects who have each of the primary and secondary renal disease diagnoses stated in the eCRF, subjects who have haemodialysis and peritoneal dialysis and the categorical calcium concentrate (mmol/L) of the dialysate currently used for the subjects. In addition, summary statistics (n, mean, standard deviation, minimum, median, and maximum) for the time since first dialysis (calculated as the difference between date of first dialysis and date of informed consent or assent, truncated to years) will be presented.

A listing of demographic and other baseline characteristics will be provided for all Enrolled Subjects. (**Listing 4.1**)

Renal history and diagnosis information including primary renal disease diagnosis, secondary renal disease diagnosis, date of first dialysis, type of dialysis, and the current calcium concentration of the dialysate the subject is using will also be listed for all Enrolled Subjects. **(Listing 4.2)**

Medical history including verbatim term, date of onset, and date resolved (or whether it was ongoing) will be listed for all Enrolled Subjects. **(Listing 4.3)**

